6.3.12 Vital signs

6.3.12.1 Pulse and blood pressure

Blood pressure (sitting) and pulse/heart rate (sitting) must be measured for new patients at screening and for all patients at randomization, Week 1, Week 2, Months 1, 3, 6, 9, 12, and the follow-up visit. The following measures should be employed consistently for every measurement:

- All measurements must be made in the sitting position.
- The patient must be sitting still at least 5 minutes before measurement.
- An appropriately sized cuff should be used.
- The arm should be at rest without movement, preferably in a supported position.
- The arm should be kept at approximately heart level.
- At least 2 measurements should be taken
 - If the 2 measurements are generally consistent with each other (within 10 mmHg for either SBP or DBP) the last reading should be recorded in the eCRF
 - If the 2 measurements differ (ie, are not within 10 mmHg for either SBP or DBP) neither result should be recorded in the eCRF. Instead the process must be repeated.
 - This process may be repeated up to 2 more times; if at the end of the third measurement the 2 measurements still differ, then the average of the 2 measurements should be recorded in the eCRF

Note: at Visit 3 (randomization) care should be taken to record heart rate and blood pressure, which at this visit should be performed pre-dose/as an initial assessment and 1 hour post-dose/after the initial assessment (for practical purposes, this can be performed and recorded within a window from 1 hour to 90 minutes post-dose). If clinically significant BP decreases (in the judgment of the investigator or delegate) are noted at the 1-hour post-dose measurement, the BP should be repeated approximately 2 hours later before the patient leaves the clinic to ensure that the BP is within normal limits for that patient (in the judgment of the investigator or delegate). If the BP value is still significantly low by the time of potential discharge, the investigator should consider discontinuing the patient from the study (see

Sections 5.8 and 6.3.13.3), although it is recommended that the investigator consult with the Study Physician prior to discontinuing the patient.

For management of markedly abnormal heart rates or blood pressures, please refer to Sections 5.8 and 6.3.13.3.

6.3.12.2 Body temperature, respiratory rate, and weight

Body temperature, respiratory rate, and weight will be measured for new patients at screening and for all patients at randomization, Month 6, and Month 12.

6.3.13 Other safety assessments

6.3.13.1 C-SSRS

The C-SSRS is a unique, simple, and short method of assessing both behavior and ideation that tracks all suicidal events, and provides a summary of suicidality (Posner et al 2007). It assesses the lethality of attempts and other features of ideation (frequency, duration, controllability, reasons for ideation, and deterrents), all of which are significantly predictive of completed suicide.

The C-SSRS will be administered at all study visits by a trained rater. The trained rater will record the clinical observation on the scale, which will be used as the source document. If at all possible, the same individual should perform the assessment at each visit to reduce scoring variability. In the event the primary rater is not available, a designated back-up rater who meets the same qualifications may perform the C-SSRS.

If a patient indicates having a rating of type 4 or 5 suicidal ideation on the C-SSRS suicidal ideation scale at any time since the previous visit when the C-SSRS was administered or indicates having had any suicidal behavior since the previous visit, the patient should be referred to a mental health professional immediately. If the C-SSRS is administered by a rater other than the PI, it is recommended that the PI confirms suicidal ideation before making a referral to mental health services, however this should not delay the referral.

6.3.13.2 Persistent or progressive severe abdominal pain

Rare cases of GI perforation associated with the use of other peripheral opioid antagonists in OIC have been reported in a post-marketing setting. Such cases of perforation have been reported to occur shortly after initiation with drug and appear to be more commonly reported in debilitated patients with multiple co-morbidities, particularly co-morbid conditions that might impair the local or global structural integrity of the GI tract (eg, cancer, peptic ulcer, pseudo-obstruction of the colon, etc.; see Section 1.4 and Section 4.2).

While abdominal pain has been reported in association with NKTR-118 use in a Phase II OIC trial, any at-risk patient who reports progressive or persistent severe abdominal pain should be evaluated immediately by the site or otherwise referred for urgent medical assessment. Other associated symptoms with abdominal pain such as fever, malaise, and or mental status changes should also mandate urgent medical evaluation.

In addition, it should be emphasized that a thorough screening abdominal/rectal examination is an important element in identifying pre-treatment findings that might identify a patient who is at high risk for perforation. The investigator should maintain a low threshold for considering abdominal x-rays, further abdominal/rectal examination, or other diagnostic aids based on clinical assessment and patient history.

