As summarized above, participation in this study may carry risks. New risks may be discovered when more patients are exposed to NKTR-118, and when NKTR-118 is delivered over a long-term period of 52 weeks. Previous studies have administered NKTR-118 for up to 4 weeks, and planned Phase III studies will administer NKTR-118 for 12 or 24 weeks (should patients participate in an optional 12 week extension study). Repeated dose toxicity has been investigated after oral administration of NKTR-118 for up to 6 months in rats and 9 months in dogs. These studies suggested no preclinical issues that would cast a doubt on the tolerability of NKTR-118 in this study. Detailed information about chronic exposure in animal studies can be found in the IB. Several steps have been taken to mitigate known and unknown risks. General safety monitoring, including AEs, vital signs, and laboratory assessments combined with exclusion of patients at higher risk for complications from experimental medication and placebo are in place to minimize any risks. ECGs will be recorded and submitted for centralized analysis at screening for new patients, and for all patients at randomization (pre-dose and post-dose/post-initial assessments), and at various time points throughout the study.

Rare cases of GI perforation associated with the use of other peripheral opioid antagonists in OIC have been reported in the post-marketing setting. Such cases of perforation may tend to occur shortly after initiation with drug and appear to be more commonly reported in debilitated patients with multiple co-morbidities, particularly co-morbid conditions that might impair the local or global structural integrity of the GI tract (eg, cancer, peptic ulcer, pseudo-obstruction of the colon, etc.). Therefore, any patient who reports progressive or persistent severe abdominal pain should be evaluated immediately by the site or otherwise referred for urgent medical assessment. Other accompanying symptoms in combination with abdominal pain such as fever, malaise, mental status changes should also mandate urgent medical evaluation. See Section 4.2 and Section 6.3.13.2 for additional guidance.

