urine pregnancy test, concomitant medications, ECG, NRS for pain, C-SSRS, modified Himmelsbach scale, and AEs) however the order of assessments in the current study should be followed. In addition, some assessments such as demographics, medical history, and laxative tolerance can be obtained from the screening visit of the previous pivotal study that the patient participated in (studies D3820C00004 or D3820C00005).

Patients who are randomized to NKTR-118 will receive a dose of NKTR-118 25 mg at Visit R1. Patients who are randomized to Usual Care will meet with the investigator at Visit R1 and start their Usual Care treatment on the same day according to the investigator's instructions.

All Patients

Visit R1 will be scheduled in the morning. Patients who receive NKTR-118 will be required to remain at the study center for a minimum of 4 hours after receiving the study drug, for observation (see Section 6.3.13.2 regarding abdominal pain), additional ECG and vital sign measurements, and completion of the modified Himmelsbach scale. Patients who receive Usual Care treatment will also be required to remain at the study center for a minimum of 4 hours after completion of initial assessments. During this time they will meet with the investigator to discuss their treatment regimen, and will undergo the same safety observations as patients in the NKTR-118 group.

Pre-dose/Initial Assessments:

- Signed informed consent prior to any study-related procedures (required for patients enrolling from a previous NKTR-118 study; already obtained for new patients)
- Signed genetic informed consent (may already have been obtained for new patients; if necessary, genetic informed consent may be signed at a subsequent visit; genetic informed consent must be obtained before any blood sample for genetic analysis is collected). Participation in the genetic component of the study is optional.
- Demographics (already obtained for new patients; obtained from the previous NKTR-118 pivotal study for rollover patients)
- Medical and surgical history including OIC history (already obtained for new patients; obtained from the previous NKTR-118 studies for rollover patients).
- LIR, LAR, LUR status (already obtained for new patients; obtained from the previous NKTR-118 pivotal study for rollover patients)

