4.2 Exclusion criteria

Patients should not enter the study if any of the following exclusion criteria are fulfilled:

1. Is receiving opioid regimen for treatment of pain related to cancer
2. History of cancer within 5 years from the screening visit with the exception of basal cell cancer and squamous cell skin cancer.
3. Medical conditions and treatments associated with diarrhea, intermittent loose stools or constipation, which could confound the interpretation of the results, eg, fecal incontinence or chronic idiopathic constipation. In addition, patients having irritable bowel syndrome (IBS) that has been previously diagnosed by a physician

██████████
prior to first initiation of opioid therapy and that meets the following criteria, would be excluded:

- Absence of a structural or biochemical explanation for the abdominal pain symptom
 - At least 12 weeks during a period of 12 months, of abdominal discomfort or pain with at least 2 of the following 3 features:
 - Relieved with defecation, and/or
 - Onset associated with a change in frequency of stool, and/or
 - Onset associated with a change in form of stool.
4. Other issues related to the GI tract that could impose risk to the patient (with a special, but not exclusive, emphasis on conditions that might impair the local or global structural integrity of the GI tract) including (but not limited to): inflammatory bowel disease (such as Crohn’s disease or ulcerative colitis), intestinal obstruction or pseudo-obstruction, suspected mechanical GI obstruction, or previous history of recurrent bowel obstruction, history of >1 episode of diverticulitis (unless treated with surgery) or clinically important active diverticular disease (as determined by the investigator), history of rectal prolapse, history of GI hemorrhage related to ongoing GI pathology (eg, ulcer), clinically important or severe peptic ulcer disease (per investigator judgment), GI ostomy, intraperitoneal catheter, history of bowel perforation, history of ischemic bowel disease or ischemic colitis, previous small bowel surgery, history of surgical stenosis, known intra-abdominal adhesions, or previous gastric by-pass surgery. In addition, patients having surgery of the colon or abdomen within 60 days of the screening period or expected surgical procedure of the abdomen during the study participation period would be excluded.

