5.8 Discontinuation from study

Patients are at any time free to discontinue from the study (IP and assessments), without prejudice to further treatment (withdrawal of consent). Such patients will always be asked about the reason(s) and the presence of any AEs. If possible, they will be seen and assessed by an investigator and Visit R15 assessments will be performed. Adverse events will be followed up (see Sections 6.3.4 and 6.3.5); and all study drugs should be returned by the patient.

Discontinued patients will not be replaced.

Patients should be discontinued in the following situations:

- Patient decision. The patient is at any time free to discontinue treatment, without prejudice to further treatment.
- Inadequate pain control after reasonable attempts to control pain have been unsuccessful
- Hepatotoxicity (significantly increased elevations in liver transaminases as defined in Section 6.3.9.2. The protocol for handling patients with elevated liver transaminases including guidelines for discontinuing patients is discussed in Section 6.3.9.2).

- Severe non-compliance to the CSP (including dosing regimen with NKTR-118 or Usual Care, and/or prescribed opioid) as judged by the investigator in consultation with the study physician
- Incorrectly enrolled patients, involving increased safety risk. The investigator should consult with the study physician before discontinuing the patient unless there is a medical urgency.
- Patient is lost to follow-up.
- The patient has a clinically significant or serious AE (eg, new or worsening heart failure) or sustained clinically significant treatment emergent abnormalities in vital signs that would not be consistent with continuation in the study, as determined by the investigator, AstraZeneca, or its representative, or the patient.
- Safety reasons as judged by the investigator.
- Patient becomes pregnant.
- Significantly worsened OIC refractory to medical treatment as judged by the investigator (including failure of the laxative rescue regimen either before or after randomization)
- The patient is unable to comply with the restrictions on the use of concomitant medications as detailed in Section 5.6 (in such cases the investigator should consult with the study physician before discontinuing the patient).
- The patient is unable to tolerate the study drug.

Abdominal pain has been reported as an AE in a previous trial with NKTR-118. The management of severe abdominal pain is discussed in Section 6.3.13.2).

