6.3.14 Safety specific areas of interest

Specific safety topics of interest for this trial include, but are not limited to, the following:

- Opioid withdrawal
- Abuse liability
- Bowel perforation type events (eg, ischemic colitis) (See Section 6.3.13.2)
- Cardiovascular type events (including, but not limited to, abnormalities in blood pressure and heart rate)

The topics listed above, as well as other topics which may be subsequently determined by AstraZeneca, will be subject to enhanced surveillance activities. Furthermore, an adjudication committee will independently assess certain of these areas of interest (ie, bowel perforation type events, cardiovascular type events, etc.). Additionally, the topics above will be analyzed for presentation in the CSR in accordance with the Statistical Analysis Plan (SAP).

Additionally, routine safety monitoring and patient risk management processes as outlined in AstraZeneca clinical trial standard operating procedures (SOPs) and in the Patient Risk Management Plan (PRMP) will be carried out to protect patients in clinical studies with NKTR-118.

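### Section 6.3.13.2 limits immediate evaluation of severe abdominal pain to undefined 'at-risk' patients, while Section 1.4 requires it for any patient

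*Protocol*

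**What the plan says.** Section 1.4 describes rare gastrointestinal perforations reported after marketing with other peripheral opioid antagonists. From this it concludes that "any patient who reports progressive or persistent severe abdominal pain should be evaluated immediately by the site or otherwise referred for urgent medical assessment". It then refers the reader to Sections 4.2 and 6.3.13.2 for more guidance.

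Section 6.3.13.2 repeats nearly the same background and gives the instruction as "any at-risk patient who reports progressive or persistent severe abdominal pain should be evaluated immediately by the site". Its next sentence carries no such limit: "Other associated symptoms with abdominal pain such as fever, malaise, and or mental status changes should also mandate urgent medical evaluation". The section also asks investigators to keep a low threshold for abdominal films, repeat examination and other diagnostic aids.

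Three other sections point to 6.3.13.2:

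- Section 3.1.2.1, for the stay of at least 4 hours after the first dose: "for observation (see Section 6.3.13.2 regarding abdominal pain".
- Section 5.8, on discontinuation: "The management of severe abdominal pain is discussed in Section 6.3.13.2".
- Section 6.3.14, among the areas of special interest: "Bowel perforation type events (eg, ischemic colitis) (See Section 6.3.13.2".

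**The concern.** Two passages in force give the same safety instruction and disagree on whom it covers. The narrower one is in the section that sites are told to consult, and the word that narrows it has no definition. Perforation is a named risk of the drug class and a specific area of interest in this trial. Section 1.4 lists abdominal pain among the most common side effects in Phase II, so the symptom will occur. At stake is whether a patient with incapacitating, continuing abdominal pain is assessed at once, or only if the site first decides that the patient belongs to a risk group the protocol has not described. With about 130 centers, different readings should be expected.

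**Working it through.** The point is textual. There is no stated figure to reproduce.

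**1. The two instructions side by side.**

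| | Section 1.4 | Section 6.3.13.2 |
|---|---|---|
| Who | any patient | any *at-risk* patient |
| Trigger | progressive or persistent severe abdominal pain | the same |
| Action | immediate evaluation by the site, or urgent referral | the same |

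Only the population differs. Both are current text and neither is redacted.

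**2. What *at-risk* could mean.** The protocol gives no definition. The paragraph before the instruction says perforation was reported more often in debilitated patients with several co-morbidities, and names three examples. The paragraph after it speaks of identifying patients at high risk of perforation. Both point to a subset. Section 4.2 treats the three named examples as follows:

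- Cancer: excluded if within 5 years, apart from basal and squamous cell skin cancer (criterion 2).
- Peptic ulcer: excluded if clinically important or severe (criterion 4).
- Pseudo-obstruction of the colon: excluded (criterion 4).

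Criterion 4 is aimed expressly at "conditions that might impair the local or global structural integrity of the GI tract". Some patients at raised risk can still enter, for example with an older cancer, a minor ulcer or a single episode of diverticulitis. On the subset reading, however, many enrolled patients would fall outside the instruction.

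**3. Where the two sections lead to different action.** Take a patient with severe persistent or progressive abdominal pain:

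| Patient | Section 1.4 | Section 6.3.13.2 |
|---|---|---|
| At risk, with associated symptoms | immediate | immediate |
| At risk, without them | immediate | immediate |
| Not at risk, with associated symptoms | immediate | urgent evaluation |
| Not at risk, without them | immediate | no timing set; low threshold for tests only |

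The instruction is lost in the last row.

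**4. Which section a site reaches.** Sections that cite 6.3.13.2 for abdominal pain or perforation: 3.1.2.1, 5.8 and 6.3.14, so 3. Of these, sections that also cite Section 1.4: 0. Section 6.3.14 concerns surveillance, adjudication and reporting more than bedside action, so 2 of the 3 are working pointers in the strict sense. Section 1.4 itself also sends its reader on to 6.3.13.2. Section 6.3.13.2 refers back to Section 1.4, but at the end of its background paragraph and not at the instruction.

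**5. Fit with the rest of the plan.** Section 3.1.2.1 cites 6.3.13.2 for the observation of every NKTR-118 patient after the first dose, with the same safety observations in the Usual Care arm. Section 6.3.13.2 says perforations were reported soon after starting drug, and more commonly, not only, in debilitated patients. Neither statement supports limiting the instruction to a subset.

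**The case against.** The strongest reply is that the sections differ in scope without conflicting. Section 6.3.13.2 does not say other patients need no evaluation, and Section 1.4 stays in force and presents 6.3.13.2 as additional guidance. A site that follows both evaluates everyone. Because 6.3.13.2 cites Section 1.4, a reader who follows that reference finds the broad instruction in the same paragraph as the risk description. This is fair, and it means the broad rule is not hidden. But the protocol does not say which wording prevails, and a site using 6.3.13.2 alone has no reason to look for a wider trigger elsewhere.

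Second, the remaining gap is narrow and partly covered. A patient in pain during the Visit R1 stay is already under observation. Section 6.3.4 defines severe as incapacitating. The low threshold for tests has no risk limit, and Section 5.8 allows discontinuation for safety. All of this stands and lowers the chance of harm. None of it sets immediate evaluation for severe pain without associated symptoms after the patient has gone home.

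Third, the qualifier might be deliberate. The sentence in 6.3.13.2 opens by noting that abdominal pain occurred with the drug in Phase II, so the aim may have been to avoid urgent referral for a common side effect. The words severe, and persistent or progressive, already serve that purpose, and Section 1.4 uses them without the qualifier.

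Finally, how sites would act is not known. That also stands.

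**Conclusion.** The inconsistency holds as stated. The same instruction covers any patient in Section 1.4 and only an undefined subset in Section 6.3.13.2, and three sections direct the reader to the narrower text. The two lead to different action for a patient with severe persistent or progressive pain, no associated symptoms, and no risk condition the site recognizes. The number of such patients cannot be derived, since the protocol gives neither a rate for this kind of pain nor the size of an at-risk group. The mismatch in wording is certain. Its practical effect rests on the assumption that some sites will read *at-risk* as a subset and work from 6.3.13.2 alone. Because other safeguards remain, this should be corrected but does not undermine the trial.

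**What to change.** Delete *at-risk* from the instruction in Section 6.3.13.2, so that it carries the Section 1.4 wording: "any patient who reports progressive or persistent severe abdominal pain should be evaluated immediately by the site or otherwise referred for urgent medical assessment". Notify sites of the correction. If the qualifier was meant to have no effect, nothing is lost by removing it.

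The change adds no visit, procedure or data collection. It does carry administrative cost. Under Section 8.5 a substantial change needs an amendment approved by each IRB and, where applicable, the national authority, and even an administrative change may need local communication or approval. With about 130 centers in up to 13 countries, it is sensible to bundle the edit with the next amendment.
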